	
localized, low grade tumors deemed cured and not treated with systemic therapy.
 
16. Subjects with a condition requiring systemic treatment with either corticosteroids (> 10 mg daily prednisone equivalents) or other immunosuppressive medications within 14 days of study drug administration. Inhaled or topical steroids, and adrenal replacement doses > 10 mg daily prednisone equivalents are permitted in the absence of active autoimmune disease.

STATISTICAL CONSIDERATIONS	
The primary endpoint for the study is 1 year landmark PFS rate. The historical control with nivo/ipi from the Checkmate 067 study is a 1 year PFS rate of ~50% [1]. The target for this study is 75% (improvement by 25%), which is deemed a clinically meaning improvement. This will require a sample size of 23 for a one sided alpha of 0.05 and the power of 0.80. A simon two stage approach will be utilized. The study will be stopped if there 7 or few subjects out of 14 subjects progression free at 1 year. If the study meets criteria for continuation to the second stage, an additional 9 subjects will be enrolled. In the final analysis, the null hypothesis will be rejected (i.e., accept the alternative hypothesis of improved efficacy with nivolumab/ipilimumab plus cabozantinib) if 16 subjects or more are progression free at 1 year of the 23 total subjects. Assuming a dropout rate of 15% during the time of study, up to 27 subjects will be enrolled.

TOTAL NUMBER OF SUBJECTS	27 enrolled subjects (23 subjects required for primary endpoint analysis)
ESTIMATED ENROLLMENT PERIOD	Estimated 18 months
ESTIMATED STUDY DURATION	Estimated 42 months (2 years beyond last patient enrolled)

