In CheckMate 067 study, 945 patients with previously untreated advanced or metastatic melanoma were randomized in a 1:1:1 ratio to receive nivolumab monotherapy, nivolumab (1mg/kg) and ipilimumab (3mg/kg) combination therapy, or ipilimumab monotherapy [1]. The study was primarily powered to demonstrate efficacy differences between nivolumab versus ipilimumab and nivolumab/ipilimumab versus ipilimumab. The observed ORRs were 43.7% in nivolumab monotherapy, 57.6% in the combination group, and 19% in ipilimumab monotherapy. Nivolumab/ipilimumab as well as nivolumab monotherapy demonstrated superior PFS and OS compared to ipilimumab monotherapy. The 12 month PFS rate was 42% and 49% in the nivolumab monotherapy and nivolumab/ipilimumab combination groups, respectively. Longer follow up showed the 3 year PFS rates were 32% and 39%, respectively. Similarly, the overall survival at 3 years was numerically higher with nivolumab/ipilimumab versus nivolumab alone (58% versus 52%).

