7.5 Treatment Response Assessment

Only those subjects who have measurable disease present at baseline, have received at least one dose nivolumab, ipilimumab and cabozantinib, and had one on-treatment scan or progressed clinically will be considered evaluable for response. These subjects will have their response classified according to the definitions stated below. Those subjects that are not evaluable for response will be replaced. Immune-Modified Response Evaluation Criteria in Solid Tumors (imRECIST) will be used for the primary response assessment and for progression free survival determination [33]. Best overall response rate will be reported. Start of treatment will define the start date for calculations of PFS and OS.

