11 STATISTICAL CONSIDERATIONS

Simon's Two-Stage Design will be used in hypothesis testing for the primary endpoint of a 1 year PFS rate. Based on the Checkmate 067 data [1], a 1 year PFS rate in the historical control is assumed to be 50% (H0: PFS rate=50%). In this trial, a target 1 year PFS rate will be 75% (improvement by 25%, H1: PFS rate \geq 75%), which is deemed a clinically meaningful improvement. This will require a sample size of 23 for a one sided alpha of 0.05 and the power of 0.80. In the futility stage with the first 14 subjects, the study will be stopped if there are 7 or fewer subjects progression free at 1 year. In the final analysis, the null hypothesis will be rejected if 16 subjects or more are progression free at 1 year of the 23 total subjects. Assuming a dropout rate of 15% during the time of study, up to 27 subjects will be enrolled.

In the event of unplanned interim analyses are needed due to slow accrual or any other reasons, we will use the curtailing based SCPRT approach for statistical analysis [36].

The PFS rate in the final analysis will be calculated and a 2-sided Clopper–Pearson 95% confidence interval (CI) will be calculated. PFS and OS will be analyzed using Kaplan–Meier product-limit estimates. Median PFS and OS and the cumulative probability of PFS and OS will be presented with two-sided 95% CI if estimable.

Remaining analyses will be descriptive and exploratory in nature. TMB will be evaluated as a continuous variable and dichotomous breakdowns including previously reported high vs low status using a 21 nonsynonymous variants/MB cutoff [37]. PD-L1 status will use high/low cutoffs of 1% and 5% positive IHC rates [1]. Other variables will be analyzed based on published data or optimization of cutoffs. Statistical comparisons will be performed with SAS/R and looking to determine associations with biomarkers and clinical outcomes.

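### The replacement rule in Section 7.5 makes no exception for death, and nothing keeps it out of the 1-year PFS test, where an early death could be replaced instead of counted as a failure

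*Combined protocol and SAP*

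**What the plan says.** Section 7.5 makes a subject evaluable only with measurable disease at baseline, at least one dose of each of the three drugs, and a post-baseline observation. On the last condition, only those who "had one on-treatment scan or progressed clinically will be considered evaluable for response". Two sentences later it says: "Those subjects that are not evaluable for response will be replaced". Death neither makes a subject evaluable nor exempts one from replacement.

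The same paragraph names imRECIST as the basis for both response and PFS, and fixes the time origin: "Start of treatment will define the start date for calculations of PFS and OS". Table 7-1 places the first scheduled on-treatment imaging at week 13.

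Section 11 tests the 1-year PFS rate in two stages. The stage 1 rule, judged on 1-year status, reads: "In the futility stage with the first 14 subjects, the study will be stopped if there are 7 or fewer subjects progression free". For the end of the trial, "the null hypothesis will be rejected if 16 subjects or more are progression free at 1 year of the 23 total subjects". The synopsis gives the numbers as "27 enrolled subjects (23 subjects required for primary endpoint analysis"), and attributes the margin to 15% dropout. Section 11 also says that "PFS and OS will be analyzed using Kaplan–Meier product-limit estimates".

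The plan does not define an analysis set for the 1-year PFS test, state that death is a PFS event, or say whether replacement under Section 7.5 applies to the 14 and 23 places.

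**The concern.** Replacement needs a target number to be restored. Response rate has none; the only required counts are the 14 and 23 of the PFS test. A study team that follows Section 7.5 literally could therefore fill a place in that test with a new subject when a treated subject dies before week 13 without recorded clinical progression, for example from toxicity. Sections 8.2.4.1.3 and 8.2.4.1.4 describe fatal haemorrhagic and thromboembolic events with cabozantinib, so such a death is foreseeable.

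In the ordinary meaning of progression-free survival, a death before 1 year is a certain failure. Replacing it cannot lower the number of successes among the 14 or the 23. It can raise that number, which makes a futility stop less likely and rejection of the null more likely. The same subject could still appear as an event in the Kaplan–Meier PFS analysis, which starts at first treatment and carries no evaluability condition, so the two PFS results could rest on different subjects.

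**Working it through.** **Inputs from Section 11.** Null rate 0.50, target rate 0.75, n1 = 14 (stop if 7 or fewer), N = 23 (reject if 16 or more), one-sided alpha 0.05, power 0.80.

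**Inputs from Section 3.3.** Historical 12-month PFS with nivolumab/ipilimumab: 49% in the study used as control, and 46-47% in the study comparing the two dose ratios.

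**Assumption.** The share e of treated subjects who would be replaced deaths is not in the documents. I use 1/27 and 2/27, that is, one or two among the planned 27.

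**Step 1: reproduce the design.** With X1 ~ Bin(14, p) and X2 ~ Bin(9, p):

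- P(stop at stage 1) = P(X1 ≤ 7)
- P(reject) = Σ over x = 8 to 14 of P(X1 = x) · P(X2 ≥ 16 − x)

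At p = 0.50, the stop probability is 0.6047 and the rejection probability 0.0462. At p = 0.75, the rejection probability is 0.8016. The stated alpha and power are reproduced.

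**Step 2: effect of replacement.** If the all-treated 1-year rate is t and a share e of treated subjects are deaths that get replaced, the success rate among those who fill the places is t/(1 − e). For t = 0.50:

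- e = 1/27: 0.50 × 27/26 = 0.5192
- e = 2/27: 0.50 × 27/25 = 0.5400

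Putting these rates into the Step 1 formulas:

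| True all-treated rate | e = 0 | e = 1/27 | e = 2/27 |
|---|---|---|---|
| 50%: P(reject) | 0.046 | 0.067 | 0.097 |
| 50%: P(stop at stage 1) | 0.605 | 0.547 | 0.484 |
| 49%: P(reject) | 0.038 | 0.055 | 0.080 |
| 47%: P(reject) | 0.024 | 0.036 | 0.054 |
| 46%: P(reject) | 0.019 | 0.029 | 0.043 |
| 75%: P(reject) | 0.802 | 0.883 | 0.944 |

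**Step 3: enrolment cap.** The formula lets replacement continue without limit. A simulation of 1,000,000 trials with at most 27 treated and t = 0.50 gives a rejection probability of about 0.067 (1 in 27) and 0.095 (2 in 27), so the cap changes little. When the deaths keep their places and count as failures, it returns 0.046.

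**Step 4: one subject at the boundary.** Suppose 15 are progression free, 7 have progressed and 1 died early: 15/23, and the null is kept. If the death is replaced by a subject who is progression free at 1 year, the result is 16/23 and the null is rejected. This shows what is possible, not how likely it is.

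**The case against.** The strongest objection is that the rule concerns response only. It stands in the response section and speaks of evaluability for response, a secondary endpoint. Section 11 refers simply to the first 14 and the 23 total subjects, with no evaluability condition and no reference back to Section 7.5. The gap between 27 and 23 already has its own explanation in the dropout allowance. A subject who has died is not progression free in ordinary usage. This stands to the extent that the link to the PFS test is a reading: the documents neither state it nor exclude it. A reader might infer that the plan removes early deaths from the primary analysis; it does not say so.

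The affected group is also narrow. Subjects with clinical progression stay evaluable, scans in induction may be brought forward (Section 8.3.6), and dose holds should not move imaging (Section 8.5). Eligibility requires ECOG 0 or 1 and excludes several bleeding and thromboembolic risks. The 18-subject triplet experience in Section 3.5 describes no death, though so small a group cannot rule out a low rate. This stands too.

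The size depends on the true rate. The induction dose ratio matches one arm of the study with 46-47% at 12 months. At those rates one replaced death in 27 keeps rejection below 0.05, and two bring it to 0.043-0.054. The 50% figures should therefore be read as the error at the plan's own null, not as a forecast.

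A reader might also infer that replacing living subjects who stop before a scan inflates the result. The documents show no direction of bias for them, and replacement unrelated to outcome leaves alpha at 0.046.

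**Conclusion.** The point holds as a conditional one. The plan contains an explicit replacement rule with no exception for death, in a paragraph that also governs PFS determination, and its only target counts belong to the 1-year PFS test. If the rule is used to fill those counts, the effect can go only one way: fewer futility stops and more rejections.

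The size is unknown because the early-death share is not given. The figures of 0.067 and 0.097 rest on two assumptions, a true all-treated rate of 50% and 1 or 2 replaced deaths in 27. They are not the trial's type I error as planned, which is 0.046. The point is worth fixing because it touches the only hypothesis test, one subject can decide the result, and the correction needs only wording. Confidence is medium, since the link between Section 7.5 and the 23 places is inferred.

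**What to change.** In Sections 7.5 and 11 and in the synopsis, state that:

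1. death from any cause before 1 year is a PFS event;
2. a treated subject who dies is not replaced and counts as not progression free in the 14 and in the 23;
3. the replacement rule for subjects not evaluable for response does not apply to the 1-year PFS test.

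The 7/14 and 16/23 rules, the sample size and the scan schedule stay as they are. With early deaths counted as failures and 23 known outcomes, alpha remains 0.046 and power 0.80. The cost is that the observed 1-year rate may be slightly lower. At a true all-treated rate of 75%, the trial rejects with the planned probability of 0.80, not the 0.88 or 0.94 that replacing 1 or 2 deaths in 27 would give; that apparent gain comes only from removing failures.

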7.5.1 Measurable Disease

Measurable disease is defined as the presence of at least one measurable lesion. Measurable lesions are defined as those that can be accurately measured in at least one dimension (longest diameter to be recorded) as >20 mm by chest x-ray, as >10 mm with CT scan, or >10 mm with calipers by clinical exam. All tumor measurements must be recorded in millimeters (or decimal fractions of centimeters).

(NOTE: Tumor lesions that are situated in a previously irradiated area might or might not be considered measurable. If the site investigator thinks it appropriate to include them, the conditions under which such lesions should be considered must be defined in the protocol).

7.5.2 Malignant lymph nodes

To be considered pathologically enlarged and measurable, a lymph node must be >15 mm in short axis when assessed by CT scan (CT scan slice thickness recommended to be no greater than 5 mm). At baseline and in follow-up, only the short axis will be measured and followed.

7.5.3 Non-measurable lesions

All other lesions (or sites of disease), including small lesions (longest diameter <10 mm or pathological lymph nodes with ≥ 10 to <15 mm short axis), are considered non-measurable disease. Bone lesions, leptomeningeal disease, ascites, pleural/pericardial effusions, lymphangitis cutis/pulmonitis, inflammatory breast disease, and abdominal masses (not followed by CT or MRI), are considered as non-measurable. Non-measurable also includes lesions that are < 20 mm by chest x-ray. NOTE: Cystic lesions that meet the criteria for radiographically defined simple cysts should not be considered as malignant lesions (neither measurable nor non-measurable) since they are, by definition, simple cysts. ‘Cystic lesions’ thought to represent cystic metastases can be considered as measurable lesions, if they meet the definition of measurability described

above. However, if non-cystic lesions are present in the same subject, these are preferred for selection as target lesions.

7.5.4 Target Lesions

All measurable lesions up to a maximum of 2 lesions per organ and 5 lesions in total, representative of all involved organs, should be identified as target lesions and recorded and measured at baseline. Target lesions should be selected on the basis of their size (lesions with the longest diameter), be representative of all involved organs, but in addition should be those that lend themselves to reproducible repeated measurements. It may be the case that, on occasion, the largest lesion does not lend itself to reproducible measurement in which circumstance the next largest lesion which can be measured reproducibly should be selected. A sum of the diameters (longest for non-nodal lesions, short axis for nodal lesions) for all target lesions will be calculated and reported as the baseline sum diameters. If lymph nodes are to be included in the sum, then only the short axis is added into the sum. The baseline sum diameters will be used as reference to further characterize any objective tumor regression in the measurable dimension of the disease. Evaluation of target lesions as per Table 7-2.

7.5.5 Non-target Lesions

All other lesions (or sites of disease) including any measurable lesions over and above the 5 target lesions should be identified as non-target lesions and should also be recorded at baseline. Measurements of these lesions are not required, but the presence, absence, or in rare cases unequivocal progression of each should be noted throughout follow-up. Non-target lesion progression does not define progression of disease. It can only contribute to defining complete response (complete disappearance required).

7.5.6 New Lesions

In contrast to RECIST v1.1, new lesions that develop during treatment are not automatically captured as progressive disease in the overall response assessment with imRECIST. New measurable lesions are incorporated into the total tumor burden using the criteria in sections 7.5.1 and 7.5.2. Non-measurable new lesions preclude complete response, but are not added to the sum of diameters calculations for response evaluation.

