7.5.7 Evaluation of Target Lesions

Table 7-2 summarizes the response evaluation by serial imaging using imRECIST. In patients with progressive disease, particularly on the first scan, it is recommended to confirm disease progression with a subsequent scan at least 4 weeks later. If the subsequent scan shows no progressive disease (lack of confirmation), patient would not be captured as having a progressive event and may continue on therapy per protocol. In patients with unequivocal disease progression as determined by the treating investigator, a confirmatory scan will not be required. In this situation, patient would discontinue therapy on study and be captured as a progressive event.

Table 7-2. Response evaluation by imRECIST:

Complete Response (CR)
	
Disappearance of all target lesions. Any pathological lymph nodes (whether target or non-target) must have reduction in short axis to <10 mm. To be assigned a status of complete response, changes in tumor measurements must be confirmed by a repeat assessment performed no less than six weeks after the criteria for response is met. This can be performed at the next scheduled scans per protocol. Patients must also have complete disappearance or normalization of lymph nodes/other non-target tumor sites (e.g. resolution of a malignant pleural effusion), and no new non-measurable lesions.

Partial Response (PR)
	
At least a 30% decrease in the sum of the diameters of target lesions, taking as reference the baseline sum diameters, as well as the addition of new measurable lesions. To be assigned a status of partial response, changes in tumor measurements must be confirmed by a repeat assessment performed no less than six weeks after the criteria for response is met. This can be performed at the next scheduled scans per protocol. Patients must also not have unequivocal progression in non-target lesions and new lesions.

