
Progressive Disease (PD)
	
At least a 20% increase in the sum of the diameters of target lesions, taking as reference the baseline tumor assessment. New measurable lesions will be added to the total sum of diameters calculation (numerator). This will be used for assessment of best overall response. In patients with tumor burden decrease followed by tumor burden increase, the nadir sum of diameters will be used for assessment of progression (i.e. the new denominator). If this occurs, an increase of 20% from nadir will used for determination of progression. The sum must also demonstrate an absolute increase of at least 5 mm. Subjects with equivocal disease progression (e.g. a new lesion in the setting of major disease regression and the absence of or improvement in disease related symptoms) should have a scan confirming disease progression at least 4 weeks following the initial scan showing imRECIST defined PD. Subjects may continue on protocol therapy until repeat scan confirms PD. If repeat scan does not confirm PD, subjects should proceed with treatment and evaluation as directed by the protocol.

Stable Disease (SD)	Neither sufficient shrinkage to qualify for PR nor sufficient increase to qualify for PD, taking as reference the smallest sum diameters while on study. NOTE: a change of 20% or more that does not increase the sum of the diameters by 5 mm or more is coded as stable disease). To be assigned a status of stable disease, response must be confirmed on a subsequent scan.
---------------------	---

The best overall response is the best response recorded from the start of the treatment until disease progression/recurrence or non-protocol therapy (taking as reference for progressive disease the smallest measurements recorded since the treatment started). The patient's best response assignment will depend on the achievement of both measurement and confirmation criteria. Table 7-3 summarizes potential outcomes.

Table 7-3. Summary of potential response outcomes by imRECIST

Target Lesions and New Measurable Lesions	Non-Target Lesions	New Lesions (Non-measurable)	Overall Response
CR	CR	No	CR
CR	Non-CR/Non-PD	Yes or No	PR
PR	Non-PD	Yes or No	PR
SD	Non-PD	Yes or No	SD
PD	Any	Yes or No	PD
Any	PD (unequivocal)	Yes or No	PD

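### The protocol contradicts itself on whether unequivocal non-target progression is a primary PFS event; the criterion behind the 50% historical rate is also unstated, and no RECIST v1.1 companion rate is planned

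*Combined protocol and SAP*

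**What the plan says.** Section 4.0 defines the primary endpoint as the 1-year PFS rate using imRECIST, and Section 7.5 names imRECIST as the criterion for determining PFS. No other criterion is given for PFS.

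On non-target lesions:

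- Section 7.5.5 asks that the presence, absence or "in rare cases unequivocal progression of each should be noted throughout follow-up". It then says "Non-target lesion progression does not define progression of disease" and, of such progression, "It can only contribute to defining complete response (complete disappearance required".
- Section 7.5.7, Table 7-3, last row: any target status combined with non-target "PD (unequivocal") gives an overall response of PD.
- Section 7.5.7, Table 7-2, PR row: "Patients must also not have unequivocal progression in non-target lesions and new lesions".

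On new lesions and confirmation:

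- Section 7.5.6 draws a contrast with RECIST v1.1: "new lesions that develop during treatment are not automatically captured as progressive disease in the overall response assessment with imRECIST". Those that are measurable enter the sum of diameters; non-measurable ones do not.
- Section 7.5.7 recommends, but does not require, a second scan no sooner than 4 weeks after apparent progression, chiefly when it appears on the first scan. For a negative second scan the rule is: "If the subsequent scan shows no progressive disease (lack of confirmation), patient would not be captured as having a progressive event". Progression that the treating investigator judges unequivocal needs no confirming scan and counts as an event.

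Section 11 tests the rate against 50%, taken from CheckMate 067, in a Simon two-stage design: stop at 7 or fewer of 14 progression free, reject H0 at 16 or more of 23. The Synopsis and Sections 2.0, 3.3 and 11 give the historical rate as about 50% or 49% without naming its response criterion. Section 11 plans a Clopper-Pearson interval and Kaplan-Meier estimates, but no PFS rate by RECIST v1.1.

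**The concern.** The primary result is a count of patients, so each patient needs one status at 1 year. Take a patient whose target lesions are stable and whose non-target disease has unequivocally progressed. Section 7.5.5 leaves that patient progression free; Table 7-3 makes the patient an event. Nothing says which passage prevails. If the choice is made once outcomes are known, it can decide the 7/14 or the 16/23 rule. One patient is 1/23 = 4.3 percentage points.

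The second issue is the comparison. In a single-arm trial the inference rests on the historical rate. If the 50% came from a criterion that counts more progressions than this trial's rules, part of an apparent gain could come from the criterion and not from adding cabozantinib. As planned, a reader could neither rule this out nor see its size.

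**Working it through.** **1. The plan's own design.** Inputs from Section 11: n1 = 14, continue if X1 ≥ 8; n2 = 9, reject if X1 + X2 ≥ 16; p0 = 0.50, p1 = 0.75.

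R(p) = Σ (x = 8 to 14) P[Bin(14, p) = x] × P[Bin(9, p) ≥ 16 − x]

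R(0.50) = 0.0462 and R(0.75) = 0.8016. The stated one-sided 0.05 and power 0.80 are reproduced.

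**2. The contradiction: one affected patient.** Fix that patient's status at s = 0 (event) or s = 1 (success) and let the other 22 be independent with rate p. With the patient in stage 1:

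R(p | s) = Σ (y with y + s ≥ 8) P[Bin(13, p) = y] × P[Bin(9, p) ≥ 16 − y − s]

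| True rate p | Coded event | Coded success |
|---|---|---|
| 0.46 | 0.0101 | 0.0301 |
| 0.50 | 0.0258 | 0.0665 |
| 0.75 | 0.6952 | 0.8371 |

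Placing the patient in stage 2 changes little (0.6994 and 0.8357 at 75%; 0.0262 and 0.0661 at 50%). Check: 0.75 × 0.8371 + 0.25 × 0.6952 = 0.8016, the design power.

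These figures are conditional on such a patient existing. A related unconditional figure is the chance of rejecting with exactly 16 of 23, where one recoded success would reverse the result: 0.148 at 75% and 0.029 at 50%.

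**3. The criterion: assumed shares only.** The documents do not say how many events imRECIST would leave out. Suppose a net share f of 1-year events by the historical criterion is not counted here, and the drug adds nothing. Then p = 1 − (1 − base)(1 − f). For base 0.50 and f = 5%: p = 1 − 0.50 × 0.95 = 0.525, and R = 0.0744.

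| Base rate (source) | f = 0% | f = 5% | f = 10% |
|---|---|---|---|
| 46% (CheckMate 511, Section 3.3) | 0.019 | 0.035 | 0.061 |
| 47% (CheckMate 511, Section 3.3) | 0.024 | 0.043 | 0.072 |
| 49% (CheckMate 067, Section 3.3) | 0.038 | 0.062 | 0.099 |
| 50% (null, Section 11) | 0.046 | 0.074 | 0.114 |

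R reaches 0.05 at p = 0.5040, so the break-even share is 1 − (1 − 0.5040)/(1 − base): 8.1%, 6.4%, 2.7% and 0.8% in the order of the table.

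Deaths cannot be reclassified. If 20% of 1-year events are deaths without prior progression (assumption), p = 1 − (1 − base)(1 − 0.8f). At base 50%, f = 5% and 10% of the remaining events then give p = 0.52 and 0.54, and R = 0.068 and 0.097.

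**The case against.** On the contradiction: Section 7.5.5 stands alone. Table 7-3, the PR row of Table 7-2 and the Section 7.5.7 text on unequivocal progression all point towards an event, and Section 7.5.5 itself calls unequivocal non-target progression rare. It may be that nobody is affected. All this stands, and it limits the expected effect. It does not remove the conflict: Section 7.5.5 mentions unequivocal progression one sentence before it denies that non-target progression defines progression, so the passages cannot be read together as saying that only unequivocal cases count.

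On the comparison, three stronger readings are tempting, and the documents support none of them.

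- A reader might infer that imRECIST here always counts the same number of progressions as RECIST v1.1, or fewer. The protocol does not reproduce RECIST v1.1 and contrasts the two explicitly only on new lesions. It also admits investigator-judged unequivocal progression (Section 7.5.7), progression by exam (Section 7.3) and clinical progression (Section 7.5), which could add events. A one-directional rule is plausible but not proved.
- A reader might infer that CheckMate 067 was assessed by RECIST v1.1. The documents do not say so.
- A reader might take 0.114 as the true type I error. It follows from an assumed 10% share at a 50% base. At the 46-47% quoted for the study that included this trial's nivolumab/ipilimumab doses, a 5% share leaves the error below 0.05.

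The looseness also has limits: confirmation is only recommended, measurable new lesions enter the sum, a 20% rise from nadir (at least 5 mm) is PD, and scans are every 12 weeks. Only patients still event-free at 1 year change the count.

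**Conclusion.** The contradiction is established from the text and touches the primary event. Its unconditional effect is unknown because the documents give no frequency for unequivocal non-target progression. Given one affected patient who is otherwise event-free at 1 year, with the other 22 independent at the stated rate, the coding moves the rejection probability between 0.70 and 0.84 at 75% and between 0.026 and 0.066 at 50%. These are not alternative values for the trial's power and type I error, which remain 0.80 and 0.046 once the event has one definition.

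The comparison point is secondary. The new-lesion and confirmation rules may make the imRECIST rate more favourable than a RECIST v1.1 rate; the criterion behind the 50% is not stated; and no planned output would show a difference. A mismatch is possible, not shown, and its size is unknown. The sample size and decision rules are sound as calculated. This should be corrected, but it does not invalidate the design.

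**What to change.** Keep imRECIST, N = 23 and the 7/14 and 16/23 rules.

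1. Before any outcome is analysed, including the 14-patient stage, reconcile Section 7.5.5 with Table 7-3 and the PR row of Table 7-2 so that the primary event has one definition.
2. In Section 11, add a descriptive 1-year PFS rate by RECIST v1.1 from the same scans, with the version and dating rule cited. Report it as a count out of 23 with its Clopper-Pearson interval. Record the first-PD date and each new lesion on the CRF even when PD is not confirmed.
3. State the criterion behind the 50%. If it is RECIST v1.1 or cannot be established, report the RECIST v1.1 count beside any claim of improvement over CheckMate 067.

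The cost is a few sentences, one derivation and one or two CRF items, with no extra scans or patients. Power stays at 0.80 for a 75% imRECIST rate. The companion rate may look less favourable, and with 23 patients it is descriptive only: the 95% intervals are 0.43-0.84 for 15/23, 0.47-0.87 for 16/23 and 0.52-0.90 for 17/23. It should not become a pass/fail test on that interval, because even 16/23, which rejects H0, gives an interval that includes 50%.
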